### **5.11 Pharmacokinetic and Biomarker Analyses**

A listing of plasma trough concentrations will be presented for the PK Analysis Set. Plasma biomarker analysis will be defined separately and will not be part of this SAP.

QMD Ref: Worldwide-TMP-ST-054-1.0 Effective: 12Aug2022	Governing QMD: Worldwide-SOP-ST-026
Confidentiality Statement	
This document is the property of Worldwide Clinical Trials Inc. and may not be duplicated, copied, altered or removed from company without prior approval from Worldwide Quality Assurance or in compliance with Worldwide Standard Operating Procedures.	

Worldwide Clinical Trials Controlled Quality Management Document		
 WORLDWIDE CLINICAL TRIALS	Sponsor:	EIP Pharma, Inc.
	Protocol Number:	EIP21-NFD-504
STATISTICAL ANALYSIS PLAN		

Note: Glial Fibrillary Acidic Protein (GFAP) and Neurofilament light (NfL) levels will be measured in pre-treatment, week 12 and week 16 and the results analyzed for treatment effects concurrently with the primary efficacy analysis.

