## **Approach for OLE Analysis**

### **Treatment groups:**

There are five treatment groups in the OLE:

Group 1 = old batch for all of OLE (or through ET), N=20

Group 2 = started OLE on old batch, switched at W16 OLE, N=35

Group 3 = started OLE on old batch, switched at W8 OLE, N=26

Group 4 = started OLE on old batch, switched at W4 OLE, N=22

Group 5 = new batch for all of OLE (or through ET), N=46

Total=149, though not all the participants above will be in the mITT analysis, with some being excluded because they do not have at least one efficacy evaluation during the OLE.

In addition, three populations will be evaluated:

1. All participants in OLE
2. OLE participants with screening plasma ptau181 <25.2 pg/mL (2.2 pg/mL in prior version of assay)
3. OLE participants with screening plasma ptau181 < 21 pg/mL (1.8 pg/mL in prior version of assay)

For OLE week 8 data point, groups 1, 2 and 3 will be pooled under “old capsule treatment” and only group 5 will be included under “new capsule treatment” (i.e. only participants with  $\geq 8$  weeks of new capsules will be included).

For the week 16 OLE analysis, groups 1 and 2 will be pooled under the label of “Old Capsules Treatment”, and groups 3, 4 and 5 will be pooled under the label of “New Capsule Treatment” (i.e. all participants with  $\geq 8$  weeks of new capsules will be included for the new capsule treatment group).

The baseline value for all change analyses will be the value at the end of the double-blind period, i.e. at week 16 of the main study (if no value, week 12 will be carried forward).

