#### *Plasma Biomarkers*

Plasma for biomarker (GFAP, NfL) were obtained at week 8 during the OLE, and will be analyzed as change from baseline (result at week 16 of the double-blind period) for participants treated with new capsules (Group 4 and Group 5 combined) vs. old capsules (Groups 1, 2 and 3; the latter because they received old capsules through to week 8).

In addition, for participants treated with placebo, a within-subject comparison will be made for change from baseline (average of screening and baseline value) to week 12 during placebo treatment compared to change from baseline for OLE (average of week 12 and week 16 of double-blind phase) to week 8 during treatment with either old or new capsules during OLE (the participants who received old vs. new capsules being analyzed separately).

The plasma biomarker data should also be the best opportunity to establish a PK-PD relationship within the participants who received the new capsules at any time within the first eight weeks (for either 4 or 8 weeks).

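### The within-subject GFAP/NfL comparison in former-placebo participants sets unscaled changes over windows of unequal length against each other, so steady marker drift alone gives a non-zero difference

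*SAP*

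**What the plan says.** Section 5.11 of the SAP states that GFAP and NfL "levels will be measured in pre-treatment, week 12 and week 16". The OLE approach at the end of the document adds, under Plasma Biomarkers: "Plasma for biomarker (GFAP, NfL) were obtained at week 8 during the OLE".

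Two biomarker analyses follow there. The first compares new with old capsules on the change from double-blind Week 16 to OLE Week 8. The second is confined to participants who had received placebo and is paired within subject:

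- placebo side, and what it is set against: "change from baseline (average of screening and baseline value) to week 12 during placebo treatment compared to change from baseline for OLE";
- OLE side: "change from baseline for OLE (average of week 12 and week 16 of double-blind phase) to week 8".

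Old- and new-capsule users are kept apart ("the participants who received old vs. new capsules being analyzed separately"). The text does not scale either change to elapsed time, adjust for time, or name a concurrent control for this second comparison.

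**The concern.** A paired comparison of two raw changes is neutral under no drug effect only if both changes cover the same length of time or the marker is flat. Here the placebo change starts at or before Day 1 and ends at Week 12. The OLE change starts, on average, at Week 14 and ends eight weeks into the extension, so the second window looks shorter. Every participant has placebo first and drug second, so the order does not balance drift out either. If GFAP or NfL moves steadily with the disease, the comparison has a built-in difference that could be read as a treatment effect.

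**Working it through.** The SAP states no window length, sample size or power for this comparison, so there is no figure of its own to reproduce. The check is arithmetic on the sampling times.

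**Inputs from the SAP**
- Placebo change: from the screening/baseline average to Week 12 (Plasma Biomarkers).
- OLE change: from the Week 12/Week 16 average to OLE Week 8 (Plasma Biomarkers).
- End of the double-blind period, used as the baseline for the OLE change analyses in general: "the value at the end of the double-blind period, i.e. at week 16 of the main study" (Treatment groups).

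**Inputs not in the SAP, taken as ranges**
- s = weeks from screening sample to baseline sample: 0 to 6.
- g = weeks from Week 16 to the first OLE dose: 0 to 2. The Week 16 baseline suggests a value near 0.
- b = drift per week, linear, with no drug effect.

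**Windows**
- Placebo: 12 − (−s + 0)/2 = 12 + s/2 weeks.
- OLE: (16 + g + 8) − (12 + 16)/2 = 24 + g − 14 = 10 + g weeks.

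**Expected difference with no drug effect**

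OLE change − placebo change = b(10 + g) − b(12 + s/2) = −b(2 + s/2 − g).

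As a share of the placebo-period change, the shortfall is (2 + s/2 − g)/(12 + s/2):

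| s (weeks) | Placebo window (weeks) | g = 0 | g = 1 | g = 2 |
|---|---|---|---|---|
| 0 | 12 | 2/12 = 16.7% | 1/12 = 8.3% | 0% |
| 2 | 13 | 3/13 = 23.1% | 2/13 = 15.4% | 1/13 = 7.7% |
| 4 | 14 | 4/14 = 28.6% | 3/14 = 21.4% | 2/14 = 14.3% |
| 6 | 15 | 5/15 = 33.3% | 4/15 = 26.7% | 3/15 = 20.0% |

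The windows are equal only when g = 2 + s/2.

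**What this could do to a test (illustration only)**

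Assume 34 pairs (half of the 22 + 46 = 68 participants in OLE Groups 4 and 5), a two-sided 5% paired z-test and g = 0. Express drift per 12 weeks in SDs of the paired difference. The shift is then drift × (2 + s/2)/12 SDs, and the rejection rates with no drug effect are:

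| Drift per 12 weeks | s = 0 | s = 4 |
|---|---|---|
| 0.25 SD | 5.7% | 7.7% |
| 0.5 SD | 7.7% | 16.3% |
| 1.0 SD | 16.3% | 49.4% |

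The spread shows how far the practical effect depends on a drift that the SAP does not give.

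**Check of the remedy**
- Change per week: b(10 + g)/(10 + g) − b(12 + s/2)/(12 + s/2) = 0 for any s and g.
- Using the Week 12/16 average as the end of the placebo period while keeping raw changes makes matters worse. The windows become 14 + s/2 against 10 weeks (g = 0), a shortfall of 4/14 = 29% at s = 0 and 7/17 = 41% at s = 6.

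**The case against.** Several points on the other side carry weight.

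- **The OLE start is not fixed in the text.** Ten weeks holds only if the first OLE dose falls at Week 16. Section 5.2.11 separates the phases by the first OLE dose, and Section 5.8 refers to follow-up until 14 days after the last dose. Neither shows a gap for participants who continue, and the Week 16 baseline points to little or none. The range from 17% to 33% is nevertheless conditional on g = 0.
- **A reader might infer that the bias favours the drug.** The SAP does not support that. It gives no sign or rate of drift for either marker. Falling markers would give the appearance of harm, and flat markers no artefact. Also, with g = 0, about 2 of the 10 OLE weeks precede the first OLE dose, which dilutes any true effect.
- **A reader might infer that this comparison underpins the PK-PD argument.** The PK-PD sentence in the same section concerns the biomarker data in participants who received new capsules in the first eight weeks. It does not refer to the within-subject comparison.
- **Protection exists elsewhere.** The new versus old capsule analysis runs from Week 16 to OLE Week 8 in both groups, so its windows are equal and its comparator concurrent. The artefact would appear in old- and new-capsule users alike, so a careful reader might notice it. But the within-subject analysis reports the two groups separately and plans no contrast between them.
- **Week 12 is a reasonable end point on raw changes.** Of the available sampling times, it gives the placebo window closest to the OLE window. The placebo-then-drug order is inherent in the extension and is not a drafting error.
- **Section 5.11 places plasma biomarker analysis outside the SAP.** The OLE approach in the same document does define this comparison, so it can be reviewed there.

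These points limit the size, direction and importance of the problem. They do not make the two windows equal.

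**Conclusion.** The point holds in a limited form. As written, the comparison has a non-zero expected difference under steady drift and no drug effect, unless the gap before the OLE happens to equal 2 + s/2 weeks. The shortfall in the OLE change is 17% to 33% of the placebo-period change if the OLE starts at Week 16 and the screening interval is 0 to 6 weeks. It is 0% to 33% if a gap of up to 2 weeks is allowed. These figures assume linear drift and are relative: the absolute size cannot be stated and could be small.

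The scope is one additional biomarker analysis. A correction is worthwhile because it is specific and cheap, not because any main conclusion of the trial depends on it.

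**What to change.** In the Plasma Biomarkers section, replace the comparison of raw changes by change per week. Divide each change by the actual weeks between its sample dates, using the mean date where two samples are averaged. Compare the two rates within subject, separately for old and new capsules as already planned. State the assumption of linear change within each period.

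The Week 12/16 average may also serve as the end of the placebo period, but only together with per-week scaling.

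An optional alternative is a mixed model on all values at actual sample dates, piecewise linear with a knot at the first OLE dose, reporting the difference in slope. It would separate the pre-drug weeks in the OLE window from the weeks on drug. However, the plan describes only one OLE biomarker time point (Week 8), so the OLE slope would rest on that value and the fitted level at the knot.

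The cost is revised wording and reprogramming of one analysis, with no new samples. The downside is the linearity assumption.
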